7.4 Diet, Fluid, Activity Control and Treatment Facilities

The subject will be asked not to make changes to dietary, exercise, or smoking habits and not to enter a weight loss program during his/her participation in the study. Subjects will be warned that cyclobenzaprine, especially when used with alcohol or other CNS depressants, may impair mental and/or physical abilities required for performance of hazardous tasks, such as operating machinery or driving a motor vehicle.

7.5 Criteria for Discontinuation or Withdrawal of a Subject

The primary reason for discontinuation or withdrawal of the subject from the study or study medication should be recorded in the case report form ([e]CRF) using the following categories. For screen failure subjects, refer to Section 9.1.12.

1. Pretreatment event (PTE) or adverse event (AE). The subject has experienced a PTE or AE that requires early termination because continued participation imposes an unacceptable risk to the subject's health or the subject is unwilling to continue because of the PTE or AE.

- Liver Function Test (LFT) Abnormalities

Study medication should be discontinued immediately with appropriate clinical follow-up (including repeat laboratory tests, until a subject's laboratory profile has returned to normal/baseline status, see Section 9.1.9), if the following circumstances occur at any time during study medication treatment:

- alanine aminotransferase (ALT) or aspartate aminotransferase (AST) $>8 \times$ upper limit of normal (ULN), or
- ALT or AST $>5 \times$ ULN and persists for more than 2 weeks, or
- ALT or AST $>3 \times$ ULN in conjunction with elevated total bilirubin $>2 \times$ ULN or international normalized ratio (INR) >1.5 , or
- ALT or AST $>3 \times$ ULN with appearance of fatigue, nausea, vomiting, right upper quadrant pain or tenderness, fever, rash and/or eosinophilia ($>5\%$).

2. Significant protocol deviation. The discovery postrandomization that the subject failed to meet protocol entry criteria or did not adhere to protocol requirements, and continued participation poses an unacceptable risk to the subject's health.
3. Lost to follow-up. The subject did not return to the clinic and attempts to contact the subject were unsuccessful. Attempts to contact the subject must be documented.
4. Voluntary withdrawal. The subject (or subject's legally acceptable representative) wishes to withdraw from the study. The reason for withdrawal, if provided, should be recorded in the (e)CRF.

Note: All attempts should be made to determine the underlying reason for the withdrawal and, where possible, the primary underlying reason should be recorded (ie, withdrawal due to an AE or lack of efficacy).

5. Study termination. The sponsor, IRB, IEC, or regulatory agency terminates the study.
6. Pregnancy. The subject is found to be pregnant.

Note: If the subject is found to be pregnant, the subject must be withdrawn immediately. The procedure is described in Section 9.1.11.

7. Lack of efficacy. The necessity to use rescue medication (any analgesics) AND/OR the investigator has determined that the subject is not benefiting from investigational treatment and, continued participation would pose an unacceptable risk to the subject.

8. Other.

Note: The specific reasons should be recorded in the "specify" field of the (e)CRF.

CONFIDENTIAL

7.6 Procedures for Discontinuation or Withdrawal of a Subject

The investigator may discontinue a subject's study participation at any time during the study when the subject meets the study termination criteria described in Section 7.5. In addition, a subject may discontinue his or her participation without giving a reason at any time during the study. Should a subject's participation be discontinued, the primary criterion for termination must be recorded by the investigator. In addition, efforts should be made to perform all procedures scheduled for the Early Termination Visit. Discontinued or withdrawn subjects will not be replaced.

8.0 CLINICAL TRIAL MATERIAL MANAGEMENT

[figure not shown]
This section contains information regarding all medication and materials provided directly by the sponsor, and/or sourced by other means, that are required by the study protocol, including important sections describing the management of clinical trial material.

8.1 Study Medication and Materials

8.1.1 Dosage Form, Manufacturing, Packaging, and Labeling

8.1.1.1 Investigational drug

Cyclobenzaprine HCl is a skeletal muscle relaxant which relieves muscle spasm of local origin without interfering with muscle function. The active ingredient in Cyclobenzaprine HCl extended-release capsules is cyclobenzaprine hydrochloride, USP. Cyclobenzaprine hydrochloride (HCl) is a white, crystalline tricyclic amine salt with the empirical formula $C_{20}H_{21}N \cdot HCl$ and a molecular weight of 311.9. It has a melting point of $217^{\circ}C$, and a pK_a of 8.47 at $25^{\circ}C$. It is freely soluble in water and alcohol, sparingly soluble in isopropanol, and insoluble in hydrocarbon solvents. If aqueous solutions are made alkaline, the free base separates. Cyclobenzaprine HCl is designated chemically as 3-(5*H*-dibenzo[*a,d*] cyclohepten-5-ylidene)-*N,N*-dimethyl-1-propanamine hydrochloride, and has the following structural formula:

Cyclobenzaprine HCl capsules contain the following inactive ingredients: diethyl phthalate NF, ethylcellulose NF (Ethocel Standard 10 Premium), gelatin, Opadry[®] Clear YS-1-7006, sugar spheres NF (20-25 mesh), and titanium dioxide. Cyclobenzaprine HCl 15 mg capsules also contain D&C yellow #10, FD&C green #3, and FD&C red #40.

The detailed information about the Drug, including list of AE is presented in the Protocol Appendix E.

8.1.1.2 Rescue Medication

NSAIDs, topical over-the-counter medications and other analgesics will be allowed as rescue therapy only and to be used before the subject is discontinued due to lack of efficacy.

8.1.1.3 Sponsor-Supplied Drug

Sponsor-supplied drugs referenced in other sections of the protocol include the following:

Cyclobenzaprine ER (CER) 15 mg and Placebo will be supplied to the study sites as identical, similar size, opaque, white capsules packed into 40 cubic centimeters High Density Polyethylene bottles, containing 60 capsules. To avoid any overdose each study subjects will receive one 40 cubic centimeters High Density Polyethylene bottles, containing 20 capsules with CER 15 mg or Placebo,

according to their randomized treatment assignment according to the procedure outlined in Section 9.3.2.

8.1.2 Storage

Investigational drug must be kept in an appropriate, limited-access, secure place until it is used or returned to the sponsor or designee for destruction. Investigational drug must be stored under the conditions specified on the label, and remain in the original container until dispensed. A daily temperature log of the drug storage area must be maintained every working day.

8.1.3 Dose and Regimen

Table 8.a Dose and Regimen

Treatment Group	Dose	Treatment Description	
		Active	Placebo
A	Placebo QD	N/A	1 capsule of placebo, orally
B	Cyclobenzaprine 15 mg QD	1 capsule containing 15 mg of Cyclobenzaprine HCl Modified-Release, orally	N/A

8.1.4 Overdose

An overdose is defined as a known deliberate or accidental administration of investigational drug, to or by a study subject, at a dose above that which is assigned to that individual subject according to the study protocol.

All cases of overdose (with or without associated AEs) will be documented on an Overdose page of the (e)CRF, in order to capture this important safety information consistently in the database. Cases of overdose without manifested signs or symptoms are not considered AEs. AEs associated with an overdose will be documented on AE CRF(s) according to Section 10.0, Pretreatment Events and Adverse Events.

Serious adverse events (SAEs) associated with overdose should be reported according to the procedure outlined in Section 10.2.2, Collection and Reporting of SAEs.

In the event of drug overdose, the subject should be treated in accordance with the compound-specific instructions.

All of the cases of cyclobenzaprine HCl overdose which were reported to five regional poison centers were reviewed for the years 1989 to 1993. A total of 750 charts were identified with cyclobenzaprine HCl exposure; and of these, 523 charts had sufficient data for evaluation. There were 121 cases in which multiple drugs were involved, and 402 cases involving only the ingestion of cyclobenzaprine HCl. The ages of the patients ranged from 7 months to 77 years with a mean of 20 years; and children

6-years-old or younger comprised 26% of the overdose cases. Overall, 63% of the patients were females.

None of the overdosed patients died. The most common adverse effects were lethargy, sinus tachycardia, and agitation. Both hypertension and hypotension were observed. Other than sinus tachycardia, dysrhythmias occurred infrequently; and none were life-threatening. No seizures occurred. In situations where the times of ingestion were known, any symptoms of overdose were manifested within 4 hours. The ingested doses of cyclobenzaprine HCl ranged from 5 mg to 1000 mg with a mean of 133 mg. The mean dose of cyclobenzaprine HCl ingested by asymptomatic patients was 45 mg, and the mean dose of cyclobenzaprine HCl ingested by symptomatic patients was 183 mg [Spiller HA, Winter ML, Mann KV, Borys DJ, Muir S, Krenzlok EP. Five-year multicenter retrospective review of cyclobenzaprine toxicity. *J Emerg Med.* 1995 Nov-Dec;13(6):781-5.].

Treatment

Treatment for overdose primarily involved symptomatic and supportive care. Rapid decontamination of the gastrointestinal tract was required. The other types of therapies used included mechanical ventilation, treatment with dopamine, the administration of a fluid bolus, sedation, and Foley catheterization. Overdoses with less than 100 mg of cyclobenzaprine HCl did not require treatment beyond gastrointestinal decontamination. Therefore, the recommended treatment for cyclobenzaprine HCl overdose begins with emptying the stomach as quickly as possible by emesis followed by gastric lavage. After gastric lavage, activated charcoal may be administered. Twenty grams to 30 g of activated charcoal may be given every 4 to 6 hours during the first 24 to 48 hours after ingestion. An electrocardiogram should be taken, and close monitoring of cardiac function must be instituted if there is any evidence of dysrhythmia. Maintenance of an open airway, adequate fluid intake, and regulation of body temperature are necessary.

The intravenous administration of 1 mg to 3 mg of physostigmine salicylate is reported to reverse symptoms of poisoning by atropine and other drugs with anticholinergic activity; therefore, physostigmine may be helpful in the treatment of cyclobenzaprine HCl overdose. Because physostigmine is rapidly metabolized, the dosage should be repeated as required, particularly if life-threatening signs, such as arrhythmias, convulsions, and deep coma recur or persist after the initial dose of physostigmine.

Because physostigmine itself may be toxic, it is not recommended for routine use.⁶ Standard medical measures should be used to manage circulatory shock and metabolic acidosis. Cardiac arrhythmias may be treated with neostigmine, pyridostigmine, or propranolol. When signs of cardiac failure occur, the use of a short-acting digitalis preparation should be considered. Close monitoring of cardiac function for not less than five days is advisable.

Anticonvulsants may be given to control seizures. Dialysis is probably of no value because of the low plasma concentrations of cyclobenzaprine HCl. Since overdosage is often deliberate, patients may attempt suicide by other means during the recovery phase. Deaths by deliberate or accidental overdosage have occurred with this class of drugs.

In conclusion, cyclobenzaprine HCl does not appear to produce the life-threatening cardiovascular or neurologic effects of the cyclic antidepressants in doses less than 1 g. Lethargy and anticholinergic effects are prominent, though serious toxicity is infrequent.

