Not often: seizures, coordinatory disturbance, dysarthria, tremor, hypertension, disorientation, insomnia, depressive mood, sensation disorders, anxiety, qualm, psychosis, strange dreams, thought disorder, hallucinations, high excitation, paraesthesia, diplopia, serotonin syndrome, neuroleptic malignant syndrome, high or low libido, gait impairment, delirium, aggressive behavior, paranoia, peripheral neuropathy, Bell's palsy, change of EEG, extrapyramidal disorder;

Respiratory disorders:

Not often: dyspnea;

Disorders of skin and subcutaneous tissue:

Not often: excessive sweating, photosensibilization, alopecia;

Sensory organs disorders:

Not often: change or loss of sense of taste, sonitus;

Disorders of genitourinary system and mammary glands:

Not often: urinary frequency or delay, disturbed urination, urinary tract dilatation, impotency, edema of testicle, gynecomastia, breast augmentation, galactorrhea.

If any side effects from patient information leaflet deteriorate or any other side effects not indicated therein are observed, **call the doctor**.

Overdosage

Overdose symptoms: disturbed consciousness (drowsiness to coma), agitation, nausea, vomiting, ataxia, tremor, low or (slightly) high blood pressure, dizziness, convulsive state, sinus tachycardia or ventricular tachycardia or bradycardia, change of ECG (QT interval elongation, His bundle block, QRS complex dilatation).

Postmarketing experience of administration showed that most often overdosage with cyclobenzaprine was associated with concurrent administration of alcohol and/or other psychotropic medication, there are also several reports about fatal cases.

Based on clinical experience, it is recommended in recipes for cyclobenzaprine to prescribe as low volume of the drug as possible, enough for the next visit of patient, in order to reduce risk of intended overdose.

Treatment: symptomatic and supportive therapy. Specific antidotes are not known. Continuous monitoring of vital functions is recommended (breathing, blood circulation and heart rhythm). Immediate gastric lavage, administration of charcoal to induce drug absorption are recommended in case of overdose. It is not recommended to induce vomiting due to risk of vomit aspiration. Forced diuresis, dialysis, blood transfusion are inefficient.

Drug-to-drug interaction

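### Section 8.1.4 begins overdose treatment with emesis, while Appendix E of the same protocol advises against inducing vomiting, and no named source settles which applies

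*Protocol*

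**What the plan says.** Section 8.1.4 defines overdose as any known administration above the assigned dose. It says an overdosed subject should be treated under the compound-specific instructions and names no document. After a summary of a poison-centre case review, a part headed Treatment concludes that "the recommended treatment for cyclobenzaprine HCl overdose begins with emptying the stomach as quickly as possible by emesis followed by gastric lavage". Charcoal may follow the lavage.

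Appendix E, the Myorix leaflet, has its own overdosage text. On decontamination it says: "Immediate gastric lavage, administration of charcoal to induce drug absorption are recommended in case of overdose". On emesis it says: "It is not recommended to induce vomiting due to risk of vomit aspiration". It opens the clinical picture with "Overdose symptoms: disturbed consciousness (drowsiness to coma".

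Section 8.1.1.1 sends the reader to Appendix E for detailed information about the drug. That pointer is general. It does not mention overdose and does not say that the appendix prevails over the body of the protocol.

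**The concern.** In an emergency, an investigator who opens the protocol at the overdose section finds emesis as the first recommended step. The appendix gives the opposite advice and a safety reason for it. The reason fits the condition being treated: Appendix E lists impaired consciousness as a sign of overdose, and Section 8.1.4 puts lethargy among the most common effects in its case review. A drowsy subject made to vomit is exposed to the aspiration risk that Appendix E names.

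What is at stake is the safety of an individual subject. No endpoint, analysis or sample-size figure depends on this text.

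**Working it through.** No arithmetic bears on the conflict. The check is a comparison of the texts.

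1. **First step.** Section 8.1.4 has emesis, then lavage. Appendix E has lavage at once, with vomiting not to be induced. A site cannot follow both.

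2. **Conditions.** The emesis sentence sets no limit by dose or level of consciousness, so it cannot be read as applying only to alert subjects, for whom aspiration would be a lesser concern. The Appendix E warning is also unconditional. The two therefore cover the same cases.

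3. **Status of the emesis sentence.** The sentences just before it describe past cases in the past tense. This one is in the present tense, draws a conclusion from those cases, stands under the Treatment label, and is followed by directive wording on the electrocardiogram and cardiac monitoring. A site would read it as an instruction.

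4. **Which text governs.** The compound-specific instructions could be:
   - the Treatment text that follows in Section 8.1.4;
   - Appendix E, whose title calls it an instruction for medical use;
   - the Investigator's Brochure, which Section 15.1 lists among the documents for ethics review and which is not available here.

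   On the first reading the sites are sent to emesis. On the second they are sent away from it, and Section 8.1.4 still states the opposite. On the third, Section 8.1.4 and Appendix E still contradict each other inside the protocol. The contradiction needs correcting on every reading.

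5. **Extent.** Both texts support lavage, charcoal and supportive care, and neither sees value in dialysis. The direct contradiction is confined to emesis.

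6. **A separate slip.** Appendix E describes charcoal as given to induce drug absorption. In a decontamination instruction this evidently should read *reduce*. Appendix E therefore cannot simply be adopted unedited as the single overdose text.

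**The case against.** The strongest reply is that Appendix E already governs. The directive sentence in Section 8.1.4 comes before the literature summary, and if it means Appendix E, the emesis clause is only dated background drawn from a review of cases from 1989 to 1993. That reading is possible, but the protocol does not state it, and the clause is worded as a current recommendation. It can mislead even if the appendix was meant to prevail.

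A second reply is that overdose is unlikely. Dispensing is limited to 20 capsules, expressly to avoid overdose, and Section 8.1.4 concludes that serious toxicity is infrequent. This stands, and it limits the weight of the point.

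A reader might infer wider disagreement between the texts. The documents do not support that:

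- **Antidote.** Section 8.1.4 says "physostigmine may be helpful in the treatment of cyclobenzaprine HCl overdose" but adds that "it is not recommended for routine use". Appendix E says "Specific antidotes are not known". An agent used non-routinely against anticholinergic symptoms need not be a specific antidote, so both statements can be true.
- **Monitoring.** Appendix E says "Continuous monitoring of vital functions is recommended (breathing, blood circulation and heart rhythm". Section 8.1.4 asks for an electrocardiogram, for close cardiac monitoring if there is evidence of dysrhythmia, and calls at least five days of cardiac monitoring advisable. A site can do all of this.

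A reader might also take all 180 randomized subjects as exposed, because the capsules look identical and a placebo subject could be made to vomit. The text matters only for a subject who overdoses, and Section 8.5 lets the investigator break the blind when treatment requires it.

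**Conclusion.** The point holds for emesis. Section 8.1.4 recommends it as the first step, Appendix E advises against it because of aspiration, and no named source resolves the difference. The conclusion rests only on the wording of the protocol.

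Its size is one treatment step in direct conflict. The documents give no overdose rate, so the number of subjects affected cannot be estimated. Nor does the mention of fatal overdoses in Appendix E make this a frequent or grave hazard in the trial: that text links overdosage most often to alcohol or other psychotropic medication, and the case review in Section 8.1.4 reports no deaths. It is a low-frequency safety conflict that should be corrected, with no effect on the statistical design.

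**What to change.** In Section 8.1.4, delete the three words *emesis followed by*, so that lavage is the named method of emptying the stomach, and add that vomiting should not be induced. Replace the reference to compound-specific instructions with a named reference to one overdose text that the sponsor's medical team has reviewed. That review should cover both places and correct the charcoal sentence in Appendix E to say that charcoal reduces absorption.

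The review should also say whether every overdose needs stomach emptying. Under the definition in Section 8.1.4, two capsules taken together already count: 2 × 15 mg = 30 mg, which Appendix E accepts as a daily dose for some patients.

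The cost is one short medical review, a few edited sentences, one cross-reference and a notice to sites. Visits, data collection, analysis and sample size do not change.

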Appendix E Instruction for Medical Use – Myorix

THE MINISTRY OF HEALTHCARE OF THE RUSSIAN FEDERATION

PATIENT INFORMATION LEAFLET

of medicinal product for medical use

Myorix[®]

Marketing authorization number:

Trade name: Myorix[®]

International non-proprietary name: Cyclobenzaprine

Dosage form: sustained-action capsules

Formulation

One sustained-action capsule contains:

15 mg dosage:

Active ingredient: cyclobenzaprine hydrochloride - 15.0 mg

Excipients: sugar grit¹ - 109.7 mg, transparent opadry[®] YS-1-7006² - 1.2 mg, ethyl cellulose - 5.4 mg, diethyl phthalate - 0.6 mg;

Capsule coat: Iron oxide red dye - 0.2379 mg, iron oxide red dye - 0.5947 mg, titanium dioxide - 0.2942 mg, water - 5.3500 mg, gelatin - 31.5232 mg.

Identification ink: blue ink TekPrint[™] SB-6018³ trace quantity

¹sugar grit content: saccharose 68.56 - 100.38 mg, corn starch 9.32 - 41.14 mg;

²Content of transparent Opadry[®] YS-1-7006: HPMC 1.091 mg, polyethylene glycol 0.109 mg;

³Content of blue ink TekPrint[™] SB-6018: shellac, dehydrated alcohol, isopropyl alcohol, butyl alcohol, propylene glycol, concentrated solution of ammonium hydroxide, blue FD&C dye No. 2 aluminum lake, indigo carmine.

30 mg dosage:

Active ingredient: cyclobenzaprine hydrochloride - 30.0 mg

Excipients: sugar grit¹ - 87.6 mg, transparent opadry[®] YS-1-7006² - 2.4 mg, ethyl cellulose - 10.7 mg, diethyl phthalate - 1.2 mg;

Capsule coat: blue FD&C dye No. 2 - 0.1906 mg, blue FD&C dye No. 1 - 0.0003 mg, red FD&C dye No. 40 - 0.0245 mg, yellow FD&C dye No. 6 - 0.0348 mg, titanium dioxide - 0.4399 mg, water - 5.4100 mg, gelatin - 31.8999 mg.

Identification ink: Opacode[®] white ink S-1-7085⁴ trace quantity.

¹sugar grit content: saccharose 54.75 - 80.15 mg, corn starch 7.45 - 32.85 mg;

²Content of transparent Opadry[®] YS-1-7006: HPMC 2.182 mg, polyethylene glycol 0.218 mg;

⁴Content of Opacode[®] white ink S-1-7085: shellac Glaze-45 % in SD-45 alcohol, titanium dioxide, isopropyl alcohol, ammonium hydroxide 28 %, propylene glycol, N-butyl alcohol, simethicon.

Description

CONFIDENTIAL

15 mg dosage capsules.

Hard gelatin capsules with light orange to orange-brown body with blue imprint “1002-15” and light orange to orange-brown cap with blue imprint “EUR”. Capsule content - white to yellow spherical granules.

30 mg dosage capsules.

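### Section 8.1.4 starts overdose treatment with induced vomiting, while Appendix E of the same protocol advises against inducing vomiting

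*Protocol*

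**What the plan says.** Section 8.1.4 first gives a general rule: "In the event of drug overdose, the subject should be treated in accordance with the compound-specific instructions". It names no document. It then summarises a retrospective review of poison-centre cases and, under a Treatment heading, concludes that "the recommended treatment for cyclobenzaprine HCl overdose begins with emptying the stomach as quickly as possible by emesis followed by gastric lavage". Activated charcoal is offered after lavage.

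The Overdosage part of Appendix E covers the same emergency. It says "Immediate gastric lavage, administration of charcoal to induce drug absorption are recommended in case of overdose", and then "It is not recommended to induce vomiting due to risk of vomit aspiration".

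The appendix is part of the protocol and the body relies on it. Section 8.1.1.1 says "The detailed information about the Drug, including list of AE is presented in the Protocol Appendix E", and the appendix is titled "Appendix E Instruction for Medical Use".

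**The concern.** The protocol gives sites opposite advice on the first step of an emergency treatment. One text makes induced vomiting that step. The other advises against it and names the hazard, aspiration.

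The protocol's own description of overdose makes that hazard relevant. From the case review, Section 8.1.4 reports that "The most common adverse effects were lethargy, sinus tachycardia, and agitation". Appendix E lists reduced consciousness that can extend to coma, and also convulsions. Vomiting induced in a subject who is drowsy or losing consciousness is the situation in which aspiration is to be feared.

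What is at stake is the safety of a subject who overdoses. The efficacy analysis is not involved.

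**Working it through.** The protocol gives no figure to reproduce, so the check is a comparison of texts followed by a short dose calculation.

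**Comparison of the two texts**

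| Step | Section 8.1.4 | Appendix E, Overdosage |
|---|---|---|
| Induced vomiting | First step of the recommended treatment | Not recommended, because of aspiration |
| Gastric lavage | Yes, after emesis | Yes, immediately |
| Activated charcoal | May be given after lavage | Recommended |

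The texts agree on lavage, both provide for charcoal, and they conflict on emesis.

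**Is the sentence in Section 8.1.4 an instruction?** The paragraph opens in the past tense, describing what was done in the reviewed cases. It then moves to the present tense to state what treatment is recommended. The sentences that follow, on the electrocardiogram and on cardiac monitoring, are also directive. A site could reasonably read the emesis sentence as an instruction.

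**Does a condition reconcile the texts?** Neither text limits its advice by dose, time since ingestion or level of consciousness. The nearest thing to a dose threshold in Section 8.1.4 is "Overdoses with less than 100 mg of cyclobenzaprine HCl did not require treatment beyond gastrointestinal decontamination". That sentence limits treatment beyond decontamination. It sets no lower dose limit for decontamination itself.

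**Does the protocol say which text governs?** No. The general rule points to compound-specific instructions without identifying them. Appendix E is a plausible reading, but Section 8.1.4 carries its own treatment text with the opposite advice on emesis.

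**How much active drug could be taken?** Inputs are the arm sizes (Section 2.0), the dispensed bottle and 14-day course (Section 9.3.2), and the doses reported in the case review (Section 8.1.4).

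- Subjects planned to receive active drug: 90 of 180.
- Supply on Day 1: 20 capsules × 15 mg = 300 mg.
- Left after the 7th daily dose: 20 − 7 = 13 capsules; 13 × 15 mg = 195 mg.
- Left after the 8th: 12 × 15 mg = 180 mg.
- Left after the 14th: 20 − 14 = 6 capsules; 6 × 15 mg = 90 mg.
- One extra capsule in a day: 2 × 15 mg = 30 mg, a daily dose that Appendix E permits.

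The case review gives a mean ingested dose of 183 mg in symptomatic patients and 45 mg in asymptomatic ones. With full dosing, the bottle holds more than 183 mg until after the 7th dose and falls just below it after the 8th. An intake of the size that produced symptoms in the review is therefore possible during roughly the first week. At the other end, one extra active capsule or surplus placebo capsules also meet the protocol's definition of overdose, but have little toxicological weight.

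**The case against.** The strongest counter-argument is that the operative sentence in Section 8.1.4 is the general rule to follow the compound-specific instructions. If those are Appendix E, the emesis sentence is only background drawn from a published case review. This reading is possible, but the protocol nowhere states it, and the emesis sentence is worded as the recommended treatment under a Treatment heading.

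The same paragraph of Section 8.1.4 also requires an open airway to be maintained. That bears on aspiration risk, but it does not remove emesis as the first step.

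Practical weight is limited, and this stands. Supply is restricted to 20 capsules to avoid overdose. In the review, ingested doses reached 1000 mg with no deaths, and serious toxicity was infrequent. It also stands that the remark on overdoses below 100 mg reports the most that was needed; it does not require decontamination for every small overdose.

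The limit to 90 subjects applies to toxicity from active drug. Sites are blinded unless they break the code through the IVRS/IWRS, so a site could also induce vomiting in a placebo subject.

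Appendix E has a weakness of its own: read literally, its phrase about charcoal gives the wrong purpose. The two texts also differ on cardiac monitoring. These are separate matters. The sentence against inducing vomiting is clear and gives its reason.

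**Conclusion.** The concern holds. Section 8.1.4 and Appendix E give opposite advice on induced vomiting, and nothing in the protocol reconciles them or says which prevails. The step in Section 8.1.4 is one that the protocol itself warns against on safety grounds.

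The finding is confined to emesis. Its practical weight lies mainly in larger intakes of active drug among the 90 planned CER subjects, from a supply of up to 300 mg. The quantities left in the bottle assume that every scheduled dose is taken. No overdose rate is given, so no count of affected subjects is claimed. This is an inconsistency in a safety instruction that should be corrected; it has no bearing on the statistical design.

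**What to change.** In Section 8.1.4, amend the sentence on emptying the stomach so that emesis is removed and it ends: *by gastric lavage. Do not induce vomiting, because of the risk of aspiration.* Notify sites of the change.

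This keeps the step that both texts share and removes the one on which they conflict. The rest of Section 8.1.4, including the cardiac-monitoring advice, and Appendix E can stay as they are for this purpose. Section 8.1.4 should not be made to override Appendix E. Once the two texts agree on emesis, this point no longer depends on which of them is taken as the compound-specific instructions.

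The cost is one text edit and a notice to sites. Visits, endpoints and sample size do not change.
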